5.2.3 Exploratory Endpoints

Exploratory efficacy endpoints include:

- Change from Baseline in QoL as assessed by SF-36 at Week 52
- Change from Baseline in pain as assessed by BPI-SF at Weeks 13, 26, 39, and 52
- Change from Baseline in exploratory biomarkers for Gaucher disease in serum, plasma, urine, and whole blood derived leukocytes or subpopulations at Weeks 13, 26, 39, and 52

- Evaluate exploratory genomic biomarkers for Gaucher disease in whole blood at Screening (ie, *CHIT1*, gene encoding chitotrioside)
- Average VCN and ISA results in whole blood and bone marrow cells at specified time points.

Exploratory safety endpoints include:

- Change from Baseline in ovarian reserve as assessed by anti-Müllerian hormone (AMH), follicle-stimulating hormone (FSH), and luteinizing hormone (LH) (female subjects only) at Weeks 26 and 52
- Change from Baseline in menstrual cycle (female subjects only) monthly through Week 52
- Change from Baseline in sperm count, volume, sperm concentration, total motility, progressive motility, and morphology (male subjects only) at Week 52

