9.3.6 Exploratory Efficacy Measures

The following exploratory efficacy measures will be collected at the times shown in Table 4 and Table 6:

- Functional status assessed by the SF-36: The SF-36 is a 36-item, subject-reported measure yielding 8 subscale scores (Vitality, Physical Functioning, Bodily Pain, General Health Perceptions, Physical Role Functioning, Emotional Role Functioning, Social Role Functioning, and Mental Health) and 2 component summary scores (Physical Functioning and Mental Functioning).
- Pain assessed by the BPI-SF questionnaire: The BPI-SF is a 9-item self-administered questionnaire used to evaluate the severity of a subject's pain and the impact of this pain on the subject's daily functioning on an 11-point scale (ie, 0 = "no pain" to 10 = "pain as bad as you can imagine").
- Exploratory biomarkers for Gaucher disease in serum, plasma, PBLs, and urine: As
 knowledge of Gaucher disease pathophysiology and related biomarkers continues to
 evolve, serum, urine, plasma and PBL samples will be collected and archived for possible
 future non-genomic and genomic biomarker testing. Samples will be destroyed 5 years
 after the CSR is finalized.
- To assess engraftment dynamics, average VCN will be determined, and ISA performed, in whole blood and bone marrow cells at time points specified in Table 4; Table 5; and Table 6. Details on whole blood and bone marrow sample collection, processing, and shipment will be included in the Laboratory Manual for the study.

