15 APPENDICES

15.1 Schedules of Assessments: Screening through the Apheresis Period

Schedule of Assessments from Screening through the Apheresis Period Table 4:

	Study Period								
			Pre-gene]	Pre-gene Therapy Infusion	usion				,
									Early Termination / Premature
Study Assessment	Screening ^a	Baseline ^b		Mobilization ^c	zation		Apheresis	resis	Discontinuationd
Study Day [D]	I	В	M D1	M D2	M D3	M D4	A D1	A D2	-
Study Week [W]	-	-	-	-		-		-	-
Assessment Window	G09-								-
Informed consent/assent	X								
Demographics	X								
General- and Gaucher-specific medical and surgical history ^e	X								
COVID-19 testing ^{ce}						X			
Transmittable disease testing ^f	X								
Blood group (type) and screen			X						
PTT and INR	X		X						
Efficacy Assessments									
Blood sample collection for biomarkers for Gaucher disease (ie, chitotriosidase enzyme activity, lyso-Gb1 plasma levels, and GCase activity in plasma) ^g	×	×							×
Abdominal MRI ^h	X								X
Bone MRI ^h	X								X
Hemoglobin concentration, hematocrit percentage, and platelet count ⁱ	X	X							×

	Study Period								
			Pre-gene	Pre-gene Therapy Infusion	usion				
									Early Termination / Premature
Study Assessment	Screeninga	Baselineb		Mobilization	ration		Apheresis	resis	Discontinuationd
Study Day [D]	ı	В	M D1	M D2	M D3	M D4	A D1	A D2	I
Study Week [W]	!	!	-	!	1	!	1	1	!
Assessment Window	Q09-		!	1	1	1	-	-	!
Blood sample collection for GCase enzyme activity in PBLs ^j	X	Х							X
Blood sample collection for GCase enzyme activity in DBS cards	X	X							X
DXA for BMD determination ^k		X							X
Leukocytes, plasma, and urine sample collection for exploratory biomarker analysis ¹		X							X
SF-36 ^m	X	X							X
BPI-SF ^m	X	×							X
Blood sample collection for average VCN determination ⁸		X							X
Bone marrow aspirate collection for average VCN determination ^g		x							
Safety Assessments									
Physical examination	X	X							X
Weight		X							X
Height		X							
Vital signs ⁿ	X	X	X	X	X	X	X	X	X
12-lead ECG	X	X							X
CBC with differential ^o	×	X	X	×	×	X	X	X	X

Protocol No.: AVRO-RD-02-201 Amendment 6, 15 June 2022

	Study Period								
			Pre-gene 1	Pre-gene Therapy Infusion	usion				
									Early Termination / Premature
Study Assessment	Screening ^a	Baseline ^b		Mobilization ^e	ation ^c		Apheresis	esis	Discontinuation ^d
Study Day [D]	-	В	M D1	M D2	M D3	M D4	A D1	A D2	-
Study Week [W]	ŀ	!	ı	1	1	1	1	1	1
Assessment Window	G09-		-	-	1	1	1	1	1

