All AEs (including SAEs and AEs of special interest) will be recorded from the time of signing of informed consent until completion of the Week 52 assessments for the study.

w Additional samples for determination of busulfan exposure may be collected.

The COVID-19 test prior to study procedures, including mobilization, apheresis, conditioning and AVR-RD-02 gene therapy infusion, will be conducted no later than 5 days prior to the planned procedure.

Schedules of Assessments: Post-gene Therapy Infusion Follow-up Period (Study Week 1 [Day 1] through Study Week 52 [Day 365]) 15.3

Schedule of Assessments for the Post-gene Therapy Infusion Follow-up Period (Study Week 1 [Day 1] through Study Week 52 [Day 365]) Table 6:

	Stud	Study Period	iod															Early
Study Assessment	Post-	gene	Ther	apy I	nfusic	Post-gene Therapy Infusion Follow-up ^b	low-u	ρ _ρ										Termination / Premature Discontinuation ^d
Study Day [D] ^a	D1	D2	D3	D4	DS	D6	D 7	D10	D14	D30	D90	D90	D120	D150	D180	D270	D365c	
Study Week [W]a	W1	W1	W1	W1	W1	W1	W1	W2	W2	WS	6M	£1W	W18	W223	W26	6£W	w52°	
Assessment Window (Days)			-			-	-	± 1D	± 1D	± 3D	Œ∓	Œ∓	± 3D	± 3D	T 4 D	Q ∠ ∓	47D	
Efficacy Assessments ^b																		
Blood sample collection for biomarkers for Gaucher disease (ie, chitotriosidase enzyme activity and lyso-Gb1 plasma level) ^e							-					X			×	X	X	X
Abdominal MRI ^f															×	×	X	X
Bone MRIf															X	X	X	X
Hemoglobin concentration, hematocrit percentage, and platelet count ^g										X	X	X			X	X	X	X
Blood sample collection for GCase enzyme activity in DBS cards										X	X	X	×	×	X	X	X	x
Blood sample collection for GCase enzyme activity in PBL s ^{c,h}											Xţ	jΧ	Xţ	Xţ	X	X	X	X

Protocol No.: AVRO-RD-02-201 Amendment 6, 15 June 2022

	Study	Study Period	poi															Early
Study Assessment	Post-	gene	Thers	ıpy In	fusion	Post-gene Therapy Infusion Follow-up ^b	dn-we	۾ ا										I ermination / Premature Discontinuation ^d
Study Day [D] ^a	D1	D2	D3	D4	D2	D6 1	D7 I	D10	D14	D30	D90	D90	D120	D150	D180	D270	D365c	1
Study Week [W]a	W1	W1	W1	W1	W1	W1	W1	W2	W2	WS	6M	W13	W18	W223	W26	W39	W52°	!
Assessment Window (Days)		-	-	-	-	· 		± 1D =	± 1D	± 3D	4 7 D	± 7D	47D					
Blood sample collection for GCase enzyme activity in plasma (processed and frozen at the site)										X	X	x	х	X	X	×	x	X
DXA for BMD determination ⁱ																	X	X
Leukocytes, plasma, serum and urine sample collection for exploratory biomarker analysis ^j												×			×	×	×	X

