2.2.1.3. Exploratory Efficacy Endpoints

Exploratory efficacy endpoints:

- Change from Baseline in QoL as assessed by SF-36 at Week 52
- Change from Baseline in pain as assessed by BPI-SF at Weeks 13, 26, 39, and 52
- Change from Baseline in exploratory biomarkers for Gaucher disease in serum, plasma, urine, and whole blood derived leukocytes, or subpopulations at Weeks 13, 26, 39, and 52
- Evaluate exploratory genomic biomarkers for Gaucher disease in whole blood at Screening (ie, CHIT1, gene encoding chitotriosidase)
- Average VCN and ISA results in both whole blood and bone marrow cells at specified time points

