5.7.10. Change from Baseline

For safety and efficacy, CFB will be calculated as (post-baseline result – baseline result), and percentage change from baseline (%CFB) will be calculated as 100 x (post-baseline result – baseline result)/baseline result.

Changes from baseline will use Baseline (Derived), including where Baseline (Derived) uses the imputed LLQ value.

Change from baseline comparisons for categorical variables will use Baseline (Derived) and will be displayed using shift-tables that display the frequency and percentage of subjects within each category at baseline and at any specified time points.

If Baseline (Derived) is missing then the CFB and %CFB will also be set to missing, unless otherwise stated. Only subjects with a value at both the Baseline (Derived) visit and the specific post-baseline visit will be presented.

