9.4. Exploratory Efficacy Analyses

9.4.1. SF-36

Observed values and absolute change from baseline in the eight SF-36 subscale scores (i.e., Vitality, Physical Functioning, Bodily Pain, General Health Perceptions, Physical Role Functioning, Emotional Role Functioning, Social Role Functioning, and Mental Health) and 2 component summary scores (Physical Functioning and Mental Functioning) will be listed.

9.4.2. **BPI-SF**

Observed values and absolute change from baseline in BPI-SF questionnaire scores for pain severity and pain interference will be listed.

9.4.3. Exploratory biomarkers for Gaucher disease in serum, plasma, urine, and whole blood derived leukocytes, or subpopulations

Observed values and absolute change from baseline in exploratory biomarkers for Gaucher disease in serum, plasma, urine, and whole blood derived leukocytes, or subpopulations will be listed.

9.4.4. Exploratory genomic biomarkers for Gaucher disease in whole blood at Screening (ie, CHIT1, gene encoding chitotriosidase)

As knowledge of Type 1 Gaucher disease pathophysiology and related biomarkers continues to evolve, back-up plasma and urine samples will be collected and archived for possible future nongenomic and genomic biomarker testing either at specialized laboratories or a Biorepository site. These samples will be destroyed 5 years after the CSR is finalized.

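### As scheduled, exploratory-biomarker serum is drawn at four visits after infusion but not at Baseline, so the serum part of a change-from-Baseline endpoint has no reference value

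*Protocol*

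**What the plan says.** The endpoint in Protocol Section 5.2.3 is "Change from Baseline in exploratory biomarkers for Gaucher disease in serum, plasma, urine, and whole blood derived leukocytes or subpopulations", assessed at Weeks 13, 26, 39 and 52. SAP Section 2.2.1.3 repeats it with serum still named. SAP Section 9.4.3 commits to a listing: "Observed values and absolute change from baseline in exploratory biomarkers for Gaucher disease in serum, plasma, urine, and whole blood derived leukocytes, or subpopulations".

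The collection rows of the schedule do not all name the same matrices:

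- Table 4 (Protocol Section 15.1), marked at Baseline and at Early Termination: "Leukocytes, plasma, and urine sample collection for exploratory biomarker analysis".
- Table 5 (Section 15.2), covering product preparation through the infusion day: no exploratory-biomarker row.
- Table 6 (Section 15.3), marked at Weeks 13, 26, 39 and 52 and at Early Termination: "Leukocytes, plasma, serum and urine sample collection for exploratory biomarker analysis".

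Protocol Section 9.3.6 includes serum among the samples to be taken. It states no visit for it and leaves timing to the tables: "The following exploratory efficacy measures will be collected at the times shown in Table 4 and Table 6".

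**The concern.** A change from Baseline needs a Baseline value. On the schedule, three of the four named matrices have one and serum does not. A pre-treatment sample cannot be obtained later, once mobilization and conditioning have been given.

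The study has no control arm, and Protocol Section 6.2.1 says response will be assessed only relative to baseline. Post-infusion serum values alone therefore cannot answer the endpoint as worded. What is at stake is the serum component of one exploratory endpoint, and a report that may carry a declared change-from-Baseline component with no values and no prespecified explanation.

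**Working it through.** The plan gives no figure to reproduce, and no sample size, power or error rate bears on the point. The check sets the collection rows against the endpoint and then applies the SAP's derivation rules.

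**Step 1. Scheduled exploratory-biomarker draws per subject, by matrix**

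| Matrix | Screening and Baseline (Table 4) | Conditioning through infusion day (Table 5) | Weeks 13, 26, 39, 52 (Table 6) |
|---|---|---|---|
| Leukocytes | 1 (Baseline) | 0 | 4 |
| Plasma | 1 (Baseline) | 0 | 4 |
| Urine | 1 (Baseline) | 0 | 4 |
| Serum | 0 | 0 | 4 |

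**Step 2. Does the choice of baseline definition matter?** SAP Section 5.6 takes the last non-missing value before the first auxiliary medication or AVR-RD-02. Protocol Section 11.1 is looser for efficacy endpoints and accepts any value before AVR-RD-02. No exploratory serum draw is scheduled before either point, so the result is the same under both.

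**Step 3. Apply the change rule.** SAP Section 5.7.10 defines change as the post-baseline result minus the baseline result and adds: "If Baseline (Derived) is missing then the CFB and %CFB will also be set to missing". That rule allows for exceptions stated elsewhere, but SAP Section 9.4.3 states none. SAP Section 5.7.11 rules out imputation of missing data.

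Derivable changes per subject = number of post-infusion visits with a sample, if a baseline exists; otherwise 0.

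- Leukocytes, plasma, urine: baseline exists, so up to 4 of 4 each.
- Serum: no scheduled baseline, so 0 of 4.

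**Step 4. Does any other text supply the missing draw?**

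- Section 9.3.6 names serum but defers timing to Tables 4 and 6. It shows that the intention and the Table 4 row disagree; it does not schedule a Baseline draw.
- Section 9.1.9 provides for archived back-up plasma and urine, not serum.
- Serum chemistry and a serum pregnancy test are scheduled at Baseline. Chemistry is run locally, and neither document says that leftover serum from either test is kept for biomarker work.

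**The case against.** The strongest reply is that nobody chose to omit Baseline serum. Section 9.3.6 and the endpoint both name serum, and Section 9.3.6 points to both tables, so the likeliest explanation is a word dropped from one row of Table 4. The footnote to that row sends collection details to the Laboratory Manual, which is not among the documents, and sites may have drawn serum at Baseline anyway. SAP Section 5.6 would accept an unscheduled pre-treatment value. This stands: the point is an inconsistency in the written schedule, and it is not evidence about the samples held.

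Two stronger readings are tempting, and the documents support neither.

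- A reader might infer that serum change is lost for every subject. That would require knowing that no site drew Baseline serum, which the documents do not show.
- A reader might multiply 4 visits by the planned 8 to 16 subjects and speak of 32 to 64 samples without a reference value (4 × 8 = 32; 4 × 16 = 64). That assumes full planned enrolment and attendance through Week 52. SAP Section 1 says the study was stopped early, SAP Section 5.1 says no treatment-naïve subjects were enrolled, and the number infused is not given.

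It is also fair to say that little planned analysis is at risk. The samples are stored for possible future testing, no exploratory serum analyte is named, and SAP Section 9.4.3 plans only a listing. SAP Section 5.1 already prints Not Calculated where a change has no baseline, so the existing rules would give observed values with the change left blank, which is most of what the SAP correction would achieve. What they would not do is bring the endpoint wording into line with what can be derived, or tell the reader why the column is empty. The schedule itself would also remain wrong for any later use.

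**Conclusion.** The point holds for the schedule as written: 0 of 4 serum changes from Baseline can be derived for a subject whose site follows Tables 4 to 6, against up to 4 of 4 for each of plasma, urine and leukocytes. It rests on two assumptions: that the Table 4 row means what it says, and that no instruction outside the two documents adds a Baseline serum tube.

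Its reach is small. It affects one matrix of one exploratory endpoint. The two named Gaucher biomarkers in the primary and secondary endpoints, lyso-Gb1 and chitotriosidase, are measured in plasma and are scheduled at Baseline, so no primary or secondary result changes. It is still worth correcting, because a stated endpoint component cannot be derived from the stated schedule and the remedy is cheap.

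**What to change.** 1. For any further enrolment or reuse of this schedule, add serum to the exploratory-biomarker row of Table 4 at Baseline, so that it agrees with Table 6, Section 9.3.6 and the endpoint. The cost is one extra tube at the existing Baseline draw.
2. For subjects already infused, check the sample inventory and the Laboratory Manual to see whether pre-treatment serum exists.
3. If it exists, keep the endpoint as worded for those subjects. If it does not, limit SAP Sections 2.2.1.3 and 9.4.3 to observed values for serum, leave change from Baseline in place for plasma, urine and leukocytes, and record the change and its reason in SAP Section 10.4. SAP Section 1 requires SAP amendments to be made before database lock; after that, the departure belongs in the study report.

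The cost of step 3 is a wording change, with one exploratory component reported as observed values only.

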- must be completed within 3 months following the decision to discontinue. After discontinuation, every effort should be made to continue to follow the subject for safety monitoring (including any indication[s] of loss of gene therapy effect).
- Blood sample(s) will be analyzed by a central laboratory. Details on collection, processing, and shipment will be included in the Laboratory Manual for the
- Hemoglobin, hematocrit, and platelet assessments for the efficacy analysis will be tested at a central laboratory. Details on collection, processing, and shipment will be included in the Laboratory Manual for the study
- Vital signs include heart rate, blood pressure, respiratory rate, and temperature. Vital signs will be obtained with the subject supine or seated. On Day 0 of the Gene Therapy Infusion Period (ie, the day of AVR-RD-02 gene therapy infusion), vital signs must be taken pre-gene therapy infusion (window -10 minutes) and post-gene therapy infusion (window +10 minutes). Additional vital signs may be taken if clinically indicated and/or mandated per local institution practice for gene therapy infusion.
 - The CBC with differential, performed locally, includes the following: hemoglobin, hematocrit, platelet count, WBC count (total and differential), RBC count, and ANC. During the Conditioning washout period, testing should be performed daily. Samples will be tested locally.
- Assessment will include routine flow cytometric analysis of T and B cell counts as well as peripheral blood lymphocyte subsets. Panel will include: CD3, CD4, CD8, CD19, and CD16/56. Performed locally.
 - Electrolytes include sodium, potassium, chloride, bicarbonate, BUN, and serum creatinine. During the Conditioning washout period, testing should be Serum chemistry includes AST, ALT, GGT, amylase, lipase, ALP, LDH, bilirubin, calcium, albumin, phosphate, magnesium, uric acid, and glucose. performed daily. Samples will be tested locally.
- Urinalysis includes blood, glucose, protein, specific gravity, and microscopic examination (if clinically indicated). Performed locally.
- Additional blood sample collection for immunogenicity testing, RCL testing, and ISA may also take place at any time, if clinically indicated.
- hormonal laboratory assessments (eg. testosterone) will also be offered to male subjects (optional assessments), which will be analyzed locally. If test results and morphology will be collected. Samples should be collected after at least 5 days to 7 days of abstinence. Samples will be tested locally. For samples that follow institutional guidelines for further evaluation. Additional assessments of reproductive potential and/or referral to a urologist is recommended. Early For measures of reproductive potential in male subjects, sperm samples for sperm count, volume, sperm concentration, total motility, progressive motility, termination assessments of measures of reproductive potential are not required for male subjects who have had a vasectomy and sterility confirmed at the indicate reduced fertility (eg, oligospermia or azoospermia, decreased sperm motility, and/or abnormal sperm morphology), investigational sites should yield abnormal results, an additional sample must be collected and tested to confirm the initial results. Percutaneous epidydimal sperm aspiration and Baseline assessment. 딤
- For female subjects, results of the serum pregnancy test on Conditioning Day -8 must be confirmed negative prior to the administration of the test dose of busulfan on Conditioning Day -6.
- For females, monthly menstrual calendar (for all menstrual cycles beginning at the Baseline visit) by subject report will be collected at the specified study
- Measures of reproductive potential in females include AMH, FSH, and LH for assessment of ovarian reserve, which will be assessed locally. If test results indicate reduced ovarian reserve during the study, investigational sites should follow institutional guidelines for further evaluation of female subjects. Additional assessments of reproductive potential and/or referral to an endocrinologist is recommended.
- washout period). For subjects with a contraindication to levetiracetam, an alternative anticonvulsant medication (eg, benzodiazepines or valproic acid) may Levetiracetam will be administered at a dose of 1,000 mg per day beginning 2 days before administration of the busulfan test dose (ie, on Conditioning Day -8) and continuing until 1 day after administration of the 4-day busulfan administration conditioning regimen (ie, until 1 day into the Conditioning be used. Details on medication administered must be captured in the eCRF.
- A conditioning regimen of IV busulfan including a test dose of 0.8 mg/kg on Day -6 will be administered. For sites using LC-MS to perform busulfan TDM, the busulfan test dose will be administered on Day -6. The Day -4 and Day -3 busulfan dose will be PK and weight-guided based on the test dose and the

calculation generated from a web-based dose simulation program that uses measurements of busulfan in serial blood samples drawn over several hours (see busulfan dose will be PK- and weight-guided based on the test dose and the respective calculated AUC using a web-based dosing simulation program. The measurements of busulfan in serial blood samples over several hours (see footnote 't') on Conditioning Day -5 (test dose) and all subsequent Conditioning nanoparticle immunoassay kit (Saladax Biomedical, Inc.) to perform busulfan TDM, the busulfan test dose will be administered on Day -5. The Day -4 busulfan doses for Day -3, Day -2, and Day -1 will be based on an AUC calculation generated from a web-based dose simulation program that will use respective calculated AUC using a web-based dose simulation program. The busulfan doses for Conditioning Days -2 and -1 will be based on an AUC footnote 's') on Conditioning Days -6 (test dose), -4 (for the Day -2 dose), and -3 (for the Day -1 dose). For sites using the investigational automated days prior to that day's dose. If the AUC_{previous dose} is outside of ± 0% of the AUC_{darget} determined by the program, the busulfan dose will be adjusted accordingly. See Section 8.1.1.3 (and the Study Treatment Manual) for further details on busulfan dose determination.

Blood samples will be collected 1, 3, and 5 hours after busulfan dose administration on Days -4, -3, -2, and -1 for busulfan TDM for dose determination (ie, Days 4 and -3) and actual cumulative AUC calculations (ie, Days -4, -3, -2 and -1; see also footnote 'r'). Laboratories performing TDM must use validated Blood samples are to be collected 1, 3, 5, and 7 hours after busulfan test dose administration for busulfan TDM and dose determination (see footnote 'r'). methods to quantify busulfan in plasma according to GLP.

For sites using LC-MS to perform busulfan TDM, PK sampling may also be performed on Day -5 to support optimization of busulfan exposure.

Prior and concomitant medications and therapies will be recorded from the time of signing of informed consent until completion of the Week 52 assessments for the study.

All AEs (including SAEs and AEs of special interest) will be recorded from the time of signing of informed consent until completion of the Week 52 assessments for the study.

w Additional samples for determination of busulfan exposure may be collected.

The COVID-19 test prior to study procedures, including mobilization, apheresis, conditioning and AVR-RD-02 gene therapy infusion, will be conducted no later than 5 days prior to the planned procedure.

Schedules of Assessments: Post-gene Therapy Infusion Follow-up Period (Study Week 1 [Day 1] through Study Week 52 [Day 365]) 15.3

Schedule of Assessments for the Post-gene Therapy Infusion Follow-up Period (Study Week 1 [Day 1] through Study Week 52 [Day 365]) Table 6:

	Stud	Study Period	iod															Early
Study Assessment	Post-	gene	Ther	apy I	nfusic	Post-gene Therapy Infusion Follow-up ^b	low-u	ρ _ρ										Termination / Premature Discontinuation ^d
Study Day [D] ^a	D1	D2	D3	D4	DS	D6	D 7	D10	D14	D30	D90	D90	D120	D150	D180	D270	D365c	
Study Week [W]a	W1	W1	W1	W1	W1	W1	W1	W2	W2	WS	6M	£1W	W18	W223	W26	6£W	w52°	
Assessment Window (Days)			-			-	-	± 1D	± 1D	± 3D	Œ∓	Œ∓	± 3D	± 3D	T 4 D	Q ∠ ∓	47D	
Efficacy Assessments ^b																		
Blood sample collection for biomarkers for Gaucher disease (ie, chitotriosidase enzyme activity and lyso-Gb1 plasma level) ^e							-					X			×	X	X	X
Abdominal MRI ^f															×	×	X	X
Bone MRIf															X	X	X	X
Hemoglobin concentration, hematocrit percentage, and platelet count ^g										X	X	X			X	X	X	X
Blood sample collection for GCase enzyme activity in DBS cards										X	X	X	×	×	X	X	X	x
Blood sample collection for GCase enzyme activity in PBL s ^{c,h}											Xţ	jΧ	Xţ	Xţ	X	X	X	X

Protocol No.: AVRO-RD-02-201 Amendment 6, 15 June 2022

	Study	Study Period	poi															Early
Study Assessment	Post-	gene	Thers	ıpy In	fusion	Post-gene Therapy Infusion Follow-up ^b	dn-we	۾ ا										I ermination / Premature Discontinuation ^d
Study Day [D] ^a	D1	D2	D3	D4	D2	D6 1	D7 I	D10	D14	D30	D90	D90	D120	D150	D180	D270	D365c	1
Study Week [W]a	W1	W1	W1	W1	W1	W1	W1	W2	W2	WS	6M	W13	W18	W223	W26	W39	W52°	!
Assessment Window (Days)		-	-	-	-	· 		± 1D =	± 1D	± 3D	4 7 D	± 7D	47D					
Blood sample collection for GCase enzyme activity in plasma (processed and frozen at the site)										X	X	x	х	X	X	×	x	X
DXA for BMD determination ⁱ																	X	X
Leukocytes, plasma, serum and urine sample collection for exploratory biomarker analysis ^j												×			×	×	×	X
$SF-36^k$															X		X	X
BPI-SF ^{h,k}											X	X	Х	Х	X	X	X	X
Blood sample collection for average VCN determination ^e										X	×	X			×	×	×	×
Bone marrow aspirate collection for average VCN determination ^e																	×	

Page 100 of 106

Protocol No.: AVRO-RD-02-201 Amendment 6, 15 June 2022

	Stud	Study Period	poi															Early
Study Assessment	Post	gene.	Ther:	ару Іі	ıfusio	n Fol	Post-gene Therapy Infusion Follow-up ^b	p _p										I ermination / Premature Discontinuation ^d
Study Day [D] ^a	D1	D2	D3	D4	DS	9Q	D7	D10	D14	D30	D90	D90	D120	D150	D180	D270	D365c	
Study Week [W]a	W1	IM	W1	W1	W1	W1	W1	W2	W2	WS	6M	W13	W18	W22y	W26	W39	W52°	
Assessment Window (Days)	l	-	1	1	-	1	- "	± 1D	# 1D	± 3D	± 3D	± 3D	± 3D	± 3D	4 7D	± 7D	47D	!
Safety Assessments ^b																		
Physical examination	Xı	X	X	X	X	X	×			X		X			X	X	X	X
Weight	X									X					Х	X	X	X
Vital signs ^m	X^{l}	X	X	X	X	X	X			X		X			X	X	X	X
12-lead ECG															X	X	X	X
CBC with differential ⁿ	$\mathbf{X}^{\mathbf{m}}$	X	X	X	X	X	X	X	X	X	X	X^{f}	Xţ	X^{f}	X	X	X	X
G-CSF injection°												G-CS	G-CSF if ANC is $< 0.5 \times 10^9$ /L	; is < 0.5	5×10^{9} /L			
Blood sample collection for T and B cell counts ^p									X	X	X	X			X	X	X	X
Serum chemistry ^q							X		X	X	X				Х	X	X	X
Electrolytes, BUN, and serum creatinine ^q	Xm	X	X	×	×	×	×		X	X	X	X			X	X	X	X
Urinalysis ^r										X	X				X	X	X	X
Blood sample collection for immunogenicity testing ^{es}										×		×			X	×	×	×
Peripheral blood sample collection for RCL testing ^{es}												Х			X	×	X	X

Page 101 of 106

	Study Period	Peri	po															Early
Study Assessment	Post-gene Therapy Infusion Follow-up ^b	ene]	[hera	ıpy In	fusion	ı Folla	dn-w	9-										I ermination / Premature Discontinuation ^d
Study Day [D] ^a	D1	D2	D3	D4	D5	1 90	D7 I	D10	D14	D30	D90	D90	D120	D150	D180	D270	D365°	
Study Week [W]a	W1	W1	W1	W1	WI	wı v	W1	W2	W2	WS	6M	W13	W18	W223	W26	W39	w52°	
Assessment Window (Days)	i	1	-	-	-	'	+	± 1D ±	± 1D	± 3D	± 7D	T ± 2 D	47D					
Blood sample collection for ISA ^{e,s}										X	X	X			X	X	X	X
Measures of reproductive potential (males) ^t		_															X	X
Monthly menstrual calendar collection (females) ^u		_								X	X	X			X	X	X	X
Measures of reproductive potential (females) ^v															X		X	X
Continuous Monitoring Procedures	Proced	ures																
Prior and concomitant medications and therapies ^w	Continuous monitoring	snont	mon	itorinį	50													X
